#### 12.6 Reporting Procedures for All Adverse Events

All AEs (including SAEs) occurring during the trial will be reported on the running logs in the AE section of the eCRF. This includes all events from the time following Screening (Visit 1) up to and including the Safety Follow-up Visit (Visit 7), whether or not attributed to the IMP and observed by the investigator or patient.

The following information will need to be provided for all AEs:

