#### F) Action Taken with Trial Medication

This question refers to the action taken with the IMP due to an AE. The action with the IMP must be classified as follows:

- Dose Not Changed
- Dose Reduced
- Drug Interrupted
- Drug Withdrawn

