12.8.1 Adverse Events

Adverse events will be coded using MedDRA 23.0 or higher according to the version in use at time of database lock. All safety analyses will be performed by actual treatment arm and reported using the SAF. A TEAE is one that started, or worsened in severity or seriousness, following the first dose of IMP. Any adverse event that worsens or becomes serious after the first IMP dose are recorded as a separate AE, therefore for programming purposes an AE will be classified as a TEAE if it first occurs on or after the IMP Start Date and before the IMP End Date + 30 days.

All AEs will be classified during the pre-treatment period, the 24-week on-treatment period or during the follow-up period as follows:

- Events that occurred before IMP Start Date are classified as pre-treatment AEs
- Events that occurred between IMP Start Date and 30 days after IMP End Date are considered on-treatment and classified as treatment-emergent AEs (TEAEs)
- Events occurring more than 30 days after IMP End Date are classified as follow-up AEs.

The following counting rules will be applied:

- For incidence reporting, if a patient reported more than one AE that was coded to the same preferred term/system organ class within a given treatment arm, the patient will be counted only once for that specific preferred term/system organ class by treatment arm and the rules defined below will be applied.
- For TEAEs presented by action taken on IMP, the worst action taken among the events with same SOC/PT will be selected for each patient. If action taken is missing for a TEAE, the action taken "drug withdrawn" will be assigned considering the AE leads to permanent IMP discontinuation. The imputed values for action taken will be used for incidence summaries, while the actual values will be used in data listings.
- For TEAEs presented by severity, the worst severity among the events with same SOC/PT will be selected for each patient. If the severity is missing for a TEAE, then a severity of "Severe" will be assigned. The imputed values for severity assessment will be used for incidence summaries, while the actual values will be used in data listings.

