12.8.1.2 Overall Adverse Event Summary

An overall adverse event summary will provide, by treatment arm, the number of adverse events as well as the number and percentage of patients with at least AE in the following categories:

- TEAE
- TEAE related to IMP
- Confirmed or suspected COVID-19 TEAE, (as described in Section 10.23.2)
- TEAE leading to permanent IMP discontinuation
- TEAE related to IMP leading to permanent IMP discontinuation
- Serious TEAE
- Serious TEAE related to IMP
- AE with outcome of death
- AE with outcome of death related to IMP.

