12.8.1.3 All-causality Treatment-emergent Adverse Event Summaries

Descriptive presentations of TEAEs will be given by PT and SOC for the SAF. The number and percentage of patients reporting at least 1 will be provided by treatment arm. As appropriate, the number of adverse events by SOC and PT will also be added.

- All TEAEs by SOC and PT
- All TEAEs by SOC, PT and subgroups (as described in Table 9.3-3)
- *Most common TEAEs (incidence ≥ 2 % in either treatment arm) by SOC and PT
- *Most common TEAEs (incidence ≥ 2 % in either treatment arm) by SOC, and PT and subgroups (as described in Table 9.3-3)
- All TEAEs by SOC, PT and maximum severity
- All TEAEs by SOC, PT and worst action taken on IMP
- All TEAEs by SOC, PT and time of first onset of AE categorized as:
- 1-7 day, 8 to 14 days, 15 to 28 days, 29 to 42 days, 43 to 84 and > 84 days (as described in Section 10.23.3)

- All TEAEs by SOC, PT and AE duration, categorized as:
- 1-7 day, 8 to 14 days, 15 to 28 days, 29 to 42 days ,43 to 84 days ,> 84 days, ongoing, indeterminate (as described in Section 10.23.4)
- All TEAEs by SOC, PT and relationship to IMP
- All treatment-related TEAEs by SOC and PT and maximum severity
- All treatment-related TEAEs by SOC and PT and subgroups (as described in Table 9.3-3)
- All treatment-related TEAEs leading to permanent IMP discontinuation by SOC and PT
- All TEAEs leading to permanent IMP discontinuation by SOC and PT
- All TEAEs leading to permanent IMP discontinuation by SOC and PT and subgroups (as described in Table 9.3-3)
- All treatment-related TEAEs leading to permanent IMP discontinuation by SOC and PT and maximum severity
- All non-serious TEAEs by SOC and PT

* These tables will not present the number of AEs by SOC/PT per treatment arm

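### SAP 12.8.1 codes a missing action taken as drug withdrawn even for TEAEs that start after IMP End Date and for patients who completed treatment

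*SAP*

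**What the plan says.** SAP 12.8.1 classes an AE as treatment-emergent if "it first occurs on or after the IMP Start Date and before the IMP End Date + 30 days". It adds: "Events that occurred between IMP Start Date and 30 days after IMP End Date are considered on-treatment".

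For a TEAE with no recorded action on IMP, the same section says that drug withdrawn "will be assigned considering the AE leads to permanent IMP discontinuation". It continues: "The imputed values for action taken will be used for incidence summaries, while the actual values will be used in data listings". The rule sets no condition on the onset date, on whether treatment was completed, or on why IMP was stopped.

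The outputs concerned are the row "TEAE leading to permanent IMP discontinuation" in the overall summary (SAP 12.8.1.2) and, in SAP 12.8.1.3, the table by worst action taken and "All TEAEs leading to permanent IMP discontinuation by SOC and PT". SAP 12.8.2.2 has the corresponding tables for serious events.

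On data collection, Protocol 12.6 records AEs "up to and including the Safety Follow-up Visit (Visit 7), whether or not attributed to the IMP". Section F of 12.6 says "The action with the IMP must be classified as follows" and lists four options: unchanged, reduced, interrupted or withdrawn. No option for events outside dosing is listed.

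Two other parts of the SAP bear on the same fact. SAP 10.1 takes IMP End Date from the End of treatment form. SAP 12.1 tabulates completion of the treatment phase, early discontinuation of IMP and its reason.

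**The concern.** An event that starts after IMP has ended cannot be the reason IMP ended. A patient recorded as having completed treatment did not stop it permanently because of an AE. In both cases the SAP fills a blank with a value that other trial data contradict. Missing severity and missing causality are also set to the worst case, but they are judgements with no second source in the SAP. Whether and when IMP stopped has one.

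At stake is the count of patients whose IMP was stopped for an AE, a main tolerability summary. Three inconsistencies can follow:

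- The summary table can count a patient whom the disposition table shows as a completer.
- It can count an event that the listing of AEs leading to discontinuation does not support, because listings keep the actual values.
- Protocol 13.6.5.2 asks for TEAEs that were reported as having led to stopping IMP. An imputed withdrawal was not reported, yet SAP 6.2 declares no change from the protocol.

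Missing causality is set to related, so an event with both fields blank could also enter the treatment-related discontinuation table.

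**Working it through.** The plan gives no figure to reproduce here. The check sets the sections side by side and then sizes one misclassified patient.

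**1. Do post-dose TEAEs arise by design?** Yes. Visit 7 falls 14 (± 4) days after the End of Treatment or Withdrawal Visit (Protocol 9.1.5), and AEs are collected up to it. That is 10 to 18 days, all inside the 30-day window. Assuming 85 days on IMP with the last dose at the End of Treatment Visit, the post-dose share of observed TEAE time is:

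- 10 / (85 + 10) = 10.5%
- 18 / (85 + 18) = 17.5%

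Patients who stop IMP early are encouraged to stay in the trial off treatment (Protocol 9.1.4). AEs starting in their first 30 off-drug days also fall in the window.

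**2. What does the rule do in each case?** With action taken blank, there are four:

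- Onset after IMP End Date, treatment completed: coded as withdrawn. False, because dosing had already finished.
- Onset after IMP End Date, IMP stopped early: coded as withdrawn. False for this event, because IMP had already stopped.
- Onset on or before IMP End Date, treatment completed: coded as withdrawn. Contradicted by disposition.
- Onset on or before IMP End Date, IMP stopped early: coded as withdrawn. Possibly true, so a worst-case fill is defensible.

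The rule treats all four alike. Only the last is a real unknown.

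**3. Which tables take the imputed value?** The rule sits under the bullet for TEAEs presented by action taken, so the worst-action table is affected for certain. Use in the discontinuation tables is an inference: the text says the AE is considered to lead to permanent discontinuation and sends imputed values to incidence summaries. That is the natural reading, but it is not stated outright.

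**4. Does the addendum change this?** No. Addendum Table 7-1 keeps SAP 12.8.1 and 12.8.2 with named exclusions. It drops the maximum-severity version of the treatment-related discontinuation table but keeps the main discontinuation tables and the disposition section (12.1). The imputation rule is untouched.

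**5. Size.** Let k be the number of patients in an arm wrongly counted and not otherwise in the table, and n the arm size. Inflation = 100 × k / n percentage points. At the planned n = 223 (Protocol 13.1), k = 1 gives 100 × 1 / 223 = 0.45. The addendum says enrollment stopped before the planned number was reached; with a smaller n, each patient adds more. The documents give no count of blank fields, so k cannot be estimated.

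**6. After the fix.** The number of completers counted through this rule is 0. In patients who stopped early, a post-dose event can still be imputed only if its start date is partial and the recorded part does not place it after IMP End Date.

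**The case against.** The strongest reply is that blanks should be rare. Protocol 12.6 requires this information for every AE, and the action must be classified. Dose not changed can be chosen for a post-dose event. Protocol 16.3 provides a data review for omissions, with queries to sites. CRF V3.0, which the SAP cites, is not among the documents and may have another option. On this view the rule is a fallback for residual blanks, in line with the SAP's other worst-case conventions, and actual values remain traceable in the listings. The AE tables are descriptive and carry no test.

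Most of this stands, and it limits the size. It does not rescue the rule, which operates only on blanks and gives a wrong answer in three of the four cases above.

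Stronger readings are tempting, but the documents do not support them:

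- A reader might infer that post-dose events will commonly be left blank because no category fits. Nothing gives a blank rate, and the field is required and queried.
- A reader might infer that every blank adds a false discontinuation. A blank for an AE that did lead to withdrawal is coded correctly, a patient already counted adds nothing, and several blanks in one patient add at most one.
- A reader might infer that the comparison between arms is biased. That needs blanks to differ by arm, and there is no evidence of this.

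It is also fair that replacing the rule with an unknown category throughout would give up a conservative convention where withdrawal is possible. The fix therefore keeps imputation there.

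**Conclusion.** The point holds in a narrow form. For TEAEs starting after IMP End Date, and for any TEAE in a patient who completed treatment, the rule assigns a value that IMP End Date or the disposition data show to be false. The worst-action table is affected directly. The discontinuation tables are affected on the natural reading of the wording, which the SAP should confirm or rule out.

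The size is 0.45 percentage points per newly miscounted patient at 223 per arm, more in a smaller arm. No wider range is supported. The total may be small, and efficacy results are not touched. The conclusion assumes that at least some action-taken fields are blank at database lock, which is the only situation the rule addresses.

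**What to change.** In SAP 12.8.1, restrict the imputation as follows:

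- **Keep** drug withdrawn as the worst case when action taken is missing, the TEAE started on or before IMP End Date, and the patient stopped IMP early.
- **Do not impute** drug withdrawn when the AE started after IMP End Date or the disposition data show that treatment was completed. Show post-dose events as not applicable, and on-treatment events in completers as missing.
- **Partial start dates:** apply the post-dose exemption only if the recorded part of the date places onset after IMP End Date. The imputed dates in SAP Table 10.23-1 should not decide this, because a missing day can be set to the first of the month and so move a post-dose event to before IMP End Date.
- **State** whether imputed actions feed the discontinuation tables as well as the worst-action table.

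The cost is a short text change and a merge with IMP End Date and disposition data that the SAP already uses. The downside is slightly more programming and a slightly less conservative count of AE discontinuations.

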12.8.1.1 Listing of Adverse Events

All AEs, SAEs, AEs leading to IMP discontinuation and AE with outcome of death will be listed.

The listings will include subject identifier, actual IMP received, SOC, preferred term, investigator term, start and stop date of the AE, whether or not the AE was treatment emergent, duration, frequency, severity, relatedness, action taken, outcome, and seriousness of the AE. Imputed start or stop dates will not be displayed in listings of AEs. These listings will be sorted by actual treatment arm, subject identifier and onset of adverse events.

12.8.1.2 Overall Adverse Event Summary

An overall adverse event summary will provide, by treatment arm, the number of adverse events as well as the number and percentage of patients with at least AE in the following categories:

- TEAE
- TEAE related to IMP
- Confirmed or suspected COVID-19 TEAE, (as described in Section 10.23.2)
- TEAE leading to permanent IMP discontinuation
- TEAE related to IMP leading to permanent IMP discontinuation
- Serious TEAE
- Serious TEAE related to IMP
- AE with outcome of death
- AE with outcome of death related to IMP.

12.8.1.3 All-causality Treatment-emergent Adverse Event Summaries

Descriptive presentations of TEAEs will be given by PT and SOC for the SAF. The number and percentage of patients reporting at least 1 will be provided by treatment arm. As appropriate, the number of adverse events by SOC and PT will also be added.

- All TEAEs by SOC and PT
- All TEAEs by SOC, PT and subgroups (as described in Table 9.3-3)
- *Most common TEAEs (incidence ≥ 2 % in either treatment arm) by SOC and PT
- *Most common TEAEs (incidence ≥ 2 % in either treatment arm) by SOC, and PT and subgroups (as described in Table 9.3-3)
- All TEAEs by SOC, PT and maximum severity
- All TEAEs by SOC, PT and worst action taken on IMP
- All TEAEs by SOC, PT and time of first onset of AE categorized as:
- 1-7 day, 8 to 14 days, 15 to 28 days, 29 to 42 days, 43 to 84 and > 84 days (as described in Section 10.23.3)

- All TEAEs by SOC, PT and AE duration, categorized as:
- 1-7 day, 8 to 14 days, 15 to 28 days, 29 to 42 days ,43 to 84 days ,> 84 days, ongoing, indeterminate (as described in Section 10.23.4)
- All TEAEs by SOC, PT and relationship to IMP
- All treatment-related TEAEs by SOC and PT and maximum severity
- All treatment-related TEAEs by SOC and PT and subgroups (as described in Table 9.3-3)
- All treatment-related TEAEs leading to permanent IMP discontinuation by SOC and PT
- All TEAEs leading to permanent IMP discontinuation by SOC and PT
- All TEAEs leading to permanent IMP discontinuation by SOC and PT and subgroups (as described in Table 9.3-3)
- All treatment-related TEAEs leading to permanent IMP discontinuation by SOC and PT and maximum severity
- All non-serious TEAEs by SOC and PT

* These tables will not present the number of AEs by SOC/PT per treatment arm

12.8.2 Death, Serious Adverse Events and Other Significant Adverse Events

12.8.2.1 Death

All deaths recorded in the EDC as adverse events, as the result of an adverse event or as fatal outcome of an adverse event will be listed and summarized as described in Section 12.8.1 and described in depth as narrative.

Descriptive presentations of fatal TEAEs will be given by PT and SOC for the SAF. The number and percentage of patients reporting at least one fatal TEAE as well as the number of events within a given treatment arm will be provided as described below:

- All TEAEs leading to death by SOC and PT (if at least 2 patients experienced a fatal issue TEAE)
- All treatment-related TEAEs leading to death by SOC and PT (if at least 2 patients experienced a fatal issue TEAE related to IMP).

12.8.2.2 Serious Adverse Events

Descriptive presentations of serious TEAEs will be given by PT and SOC for the SAF. The number and percentage of patients reporting at least one serious TEAE, as well as the number of events, within a given treatment arm will be provided as described below:

- All serious TEAEs by SOC and PT,
- All serious TEAEs by SOC, PT and subgroups (as described in Table 9.3-3),
- All serious TEAEs leading to permanent IMP discontinuation by SOC and PT,
- All serious treatment-related TEAEs by SOC and PT,
- All serious treatment-related TEAEs by SOC and PT leading to permanent IMP discontinuation by SOC and PT.

12.8.3 Laboratory Data

The clinical safety laboratory data (hematology and biochemistry) are planned to be collected at Screening, Visit 2, Visit 4 and Visit 6.

For the purposes of summarization in both the tables and listings, all laboratory values will be converted (as needed) to SI units. The investigator and trial monitor will be provided with a list of the normal ranges used by the central clinical laboratory for all variables assessed during the trial and a statement of accreditation (or similar) for the laboratory.

Only scheduled laboratory parameters defined in Table 9.3-3 coming from central laboratory and those derived from them as eGFR (as defined in Section 10.14) will be included in summary tables. However unscheduled laboratory values (coming from central or local laboratories) will be used in abnormality summary tables and will be presented in listings (using categories as defined in Appendix 2).

Baseline, Visit 4, Visit 6, minimal, maximal and last on-treatment values along with the change from baseline to Visit 4, Visit 6, minimal, maximal and last on-treatment assessment will be summarized using the SAF, by treatment arm, separately for red blood cells parameters and white blood cells parameters, hepatobiliary parameters, renal parameters, coagulation parameters and electrolytes and proteins (as described Appendix 1). Furthermore AST, ALT, GGT, ALP and total bilirubin will also be summarized as a multiple of the upper limit of normal (ULN). The definitions for minimal and maximal values are given in Section 10.24.2 and the definition for last on-treatment value is given in Section 10.24.

Laboratory, hematology and biochemistry (as described in Appendix 1) abnormalities will be evaluated, on patients from the SAF using shift tables from baseline to the last on-treatment value and on the most extreme on-treatment value (as defined in Section 10.24.2) during the 12-week on-treatment period according to baseline status with categories based on:

- Reference ranges as either normal, below the lower limit of normal (LLN) as "Low" or above the ULN as "High"
- CTCAE toxicity grade using version 5.0 or higher (as defined in Appendix 3 for hematology parameters and in Appendix 4 for biochemistry and urinalysis parameters),

Additionally, shift tables by treatment arm on patients from the SAF will be used to present change in status category (as defined in Section 10.14) for eGFR from baseline to last on-treatment value and to the lowest value during the 12-week on-treatment period.

Furthermore, a summary of patients with laboratory values outside the reference ranges at baseline and during the 12-week on-treatment period (as defined in Section 10.2.2) will be presented for scheduled parameter including either scheduled visit only or scheduled and unscheduled visits, by treatment arm.

Regarding AST, ALT, GGT, ALP and total bilirubin these parameters will be summarized by treatment arm within the SAF for the 12-week on-treatment period using SI units and as a proportion of the population with no missing assessment if abnormal values with reference to ULN are presented using the categories as described in Table 12.8-1.

Hepatic laboratory Parameters	Abnormality criteria
ALT	> 3 x ULN
	>5 x ULN
	> 8 x ULN
	> 10 x ULN
	> 20 x ULN
AST	> 3 x ULN
	>5 x ULN
	> 8 x ULN
	> 10 x ULN
	> 20 x ULN
ALP	> 1.5 x ULN
	> 2 x ULN

Table 12.8-1 Hepatic Abnormality Criteria

	> 3 x ULN
Total bilirubin	> 1.5 x ULN
	> 2 x ULN
	> 3 x ULN
	> 5 x ULN
GGT	> 1 x ULN

ALT = alanine aminotransferase; *AST* = aspartate aminotransferase; *ALP* = alkaline phosphatase; *GGT*= gamma-glutamyl transferase.

All laboratory values will be listed and all test values outside the normal range will be flagged.

• Urinalysis results, planned to be collected at Screening and Day 85 (end of treatment) will be summarized and listed

12.8.3.1 Potential Drug-induced Liver Injury (DILI)

Liver function test data will also be provided in separate listings for:

- Patients who possibly met Hy's Law criteria (ie, had any elevated ALT or AST of >3 x ULN, and increase in total bilirubin >=2 x ULN, and ALP <2 x ULN at the same visit)
- Patients who met any one or more of the following criteria at any post-baseline visit (list laboratory parameters ALT, AST, ALP and total bilirubin only)
- ALT or AST > 3 x ULN with the appearance of fatigue, nausea, vomiting, right upper quadrant pain or tenderness, fever, rash, and/or eosinophilia (> 5%)
- ALT or AST > 8 x ULN
- ALT or AST > 5 x ULN for more than 2 weeks
- ALT or AST > 3 x ULN and (TBL > 2 x ULN or INR > 1.5).

A summary table will also be provided by treatment arm for number of patients who met any of the criteria specified above at any post-baseline visit during the 12-week on-treatment period.

All post-baseline potential drug-induced liver injury laboratory data will be listed.

12.8.4 Vital Signs

Vital signs will include sitting systolic and diastolic blood pressure (BP) and pulse rate (PR) which are planned to be measured at Screening, Visit 2, Visit 3, Visit 4, Visit 5, Visit 6, Visit 7 (FU) and for last on-treatment assessment (as defined in Section 10.2.4).

Observed and change from baseline value in vital signs measures at each scheduled timepoint (Visit 3, Visit 4, Visit 5, Visit 6), at last on-treatment assessment and at Visit 7 (FU) will be summarized by treatment arm.

The number and percentage of patients with any clinically significant change in vital signs (as defined in Table 12.8-2) during the 12-week on-treatment period will be summarized by treatment arm. Any measurement (scheduled or unscheduled), not taken in standing position, will be used to determine if any abnormality criteria is met.

Blood pressures and pulse rate criteria	Abnormality criterion value	Abnormality criterion on change from baseline
SBP	> 180 mmHg	≥ 20 mmHg increase from baseline
	< 90 mmHg	≥ 20 mmHg decrease from baseline
DBP	> 105 mmHg	≥ 15 mmHg increase from baseline
	< 50 mmHg	≥ 15 mmHg decrease from baseline
Pulse rate	> 120 bpm	≥ 10 bpm increase from baseline
	< 50 bpm	≥ 10 bpm decrease from baseline

Table 12.8-2 Blood Pressures and Pulse Rate Abnormality Criteria

SBP = Systolic blood pressure; *DBP* = diastolic blood pressure; bpm=beats per minutes to be classified as potentially clinically significant, the measurement must satisfy both criteria: the criterion for the value and the criterion for the change relative to baseline.

All vital signs will be listed.

